7.2.2 Randomization Code Creation and Procedure

Following successful completion of the run-in period, subjects will be randomized 1:1 to either GDH or comparator MR treatment. Randomization will be stratified by gender and IBS subtype. Eight separate randomization schedules will be generated to account for the stratification (Male/IBS IBS-C, Male/IBS-D, Male/IBS-M, Male/IBS-U, Female/IBS-C, Female/IBS-D, Female/IBS-M, Female/IBS-U). Additionally, continuous monitoring of enrollment will occur to ensure that at least approximately 20% of the randomized population is male and at least approximately 25% of the randomized population includes each of the three major IBS subtypes (IBS-C, IBS-D, and IBS-M). Screening of female subjects will be discontinued if approximately 270 female subjects are randomized. If randomization into a particular IBS subtype reaches approximately 144 subjects, then screening of subjects with that particular IBS subtype will be temporarily discontinued until the IBS subtypes lacking enrollment have randomized approximately 90 subjects. Finally, if randomization into the rare IBS-U subtype reaches 20 total subjects, enrollment will be discontinued for that subtype.

The randomization schedule will be prepared by an unblinded statistician before the start of the study. As this is a double-blind study, only unblinded personnel (unblinded statistician, Curebase randomization staff) will have access to the randomization schedule before official unblinding of treatment assignment post database lock.

Randomization will occur during the “Onboarding Call” when a member of the Curebase randomization staff will enter the treatment group allocation on the metaMe platform. No subject will be randomized into this study more than once. All randomization information will be stored in a secured area, accessible only by authorized personnel.

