6.5 Strategies for Recruitment and Retention

The study seeks to enroll adult subjects, ages 18 to 70 years of age, who have a confirmed diagnosis of IBS via the Rome IV diagnostic criteria. To meet the enrollment goal of approximately 380 randomized subjects and 300 evaluable subjects (estimated maximum 20% study dropout rate) patients will be recruited from participating clinic populations (study physicians will be authorized to screen their own subject population for eligibility) and subjects who have been recruited and prescreened via online, digital channels.

Planned traditional recruitment channels include:

- Distribution of flyers to our clinics
- Distribution of flyers to university health centers
- Informational outbound phone calls to subjects from study staff
- Referrals by family members of subjects to the study

Planned digital recruitment channels include:

- Social media community groups
- Facebook
- Craigslist
- Instagram

It is desirable to enroll many minorities and women and create a diverse population. 60-65% of IBS subjects are female. No special action will be employed to ensure adequate female enrollment.

Subjects will be compensated for participation in the study.

Participants will receive their compensation payments via Curebase so long as they continue to contribute data consistently. Payments will be withheld for subjects that fail to complete ≥ 5 out of 7 of the weekly abdominal pain score surveys. Participants will be provided a warning after they miss 1 of the weekly data collection points.

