9.2 Sample Size Determination

In this study, 380 subjects will be randomized in a 1:1 ratio to GDH or comparator to ensure that at least 300 subjects complete their Week 13-16 assessment for analysis. Three hundred (300) subjects completing Phase 3 will provide at least 90% power to detect an 18 percentage point difference in response rates between the GDH and comparator treatment groups at the 5% significance level. The study was powered assuming that the comparator treatment group is expected to demonstrate a 26% response rate. To determine the expected response rate in the comparator treatment group, two studies of GDH reporting data that utilized dichotomous outcome measures were examined. The first (9) used an endpoint of % treatment responders (defined as a >50% reduction in IBS-SSS). In this study, 52% of subjects in the GDH group and 26% of subjects in the control group (usual care) were responders. A more recent study by Flik et al (12) reported an "adequate relief" response rate of 40% in the GDH group compared to 17% in the Edu control group. It is believed the response rate in the comparator treatment group in this study is likely to be ~26%.

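### At 380 randomised, the subtype pause (144) and release (90) triggers in Section 7.2.2 do not secure the stated minimum of about 25% for each major IBS subtype

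*Combined protocol and SAP*

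**What the plan says.** Section 7.2.2 (Randomization Code Creation and Procedure) commits to continuous monitoring so that "at least approximately 25% of the randomized population includes each of the three major IBS subtypes" (IBS-C, IBS-D and IBS-M).

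The same paragraph gives the means:

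- Pause trigger: "If randomization into a particular IBS subtype reaches approximately 144 subjects", screening for that subtype is suspended.
- Release: the suspension lasts "until the IBS subtypes lacking enrollment have randomized approximately 90 subjects".
- IBS-U: enrolment of this subtype ends at 20.

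Section 9.2 gives the total: "380 subjects will be randomized in a 1:1 ratio to GDH or comparator". The synopsis and Section 6.5 also work with 380, in places as an approximate or minimum figure. No section explains how 144 and 90 were derived.

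**The concern.** A floor and the rule meant to enforce it stand in one paragraph, so the rule should deliver the floor at the planned total. The release level is already below 25% of 380. More importantly, the pause acts so late that two subtypes together can take most of the places before the third is protected.

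What is at stake is the size of the smallest major subtype. Stool frequency is analysed only in IBS-C (Section 9.4.3.4), and stool consistency response only in IBS-D and IBS-M (Section 9.4.3.3). Section 9.4.8 repeats the primary and secondary analyses by subtype, and by IBS drug therapy within IBS-C and within IBS-D.

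**Working it through.** **Inputs.** N = 380 (Section 9.2). Floor 25% per major subtype, pause at 144, release at 90, IBS-U cap 20 (all Section 7.2.2). Dropout at most 20% (Section 6.5). IBS-U is described as under 5% of patients (Section 3.1).

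**Step 1: the floor as a count.** 0.25 × 380 = 95. The plan's 90 does not reproduce this: 90/380 = 23.7%, which is 5 subjects or 1.3 percentage points short.

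**Step 2: the worst case of the pause rule.** Places left for the third subtype = 380 − 144 − 144 − (number of IBS-U).

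| IBS-U randomised | Places left | Share of 380 |
|---|---|---|
| 0 | 92 | 24.2% |
| 2 | 90 | 23.7% |
| 20 (cap) | 72 | 18.9% |

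With more than 2 IBS-U subjects, the third subtype cannot reach its own release level of 90 within 380. At the cap it falls 95 − 72 = 23 subjects short of the floor.

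**Step 3: how extreme the case must be.** With one subtype at 144 and IBS-U at 20, the other two share 380 − 144 − 20 = 216 places. The smaller drops below 95 once the larger passes 216 − 95 = 121, and below 90 once it passes 216 − 90 = 126. The second subtype therefore need not reach its own trigger for the floor to be missed.

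Since 144/380 = 37.9%, subjects arriving steadily in proportions 37.9 : 37.9 : 18.9 : 5.3 would reach the pause only as the last places fill. In that mix the rule changes nothing.

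**Step 4: consequence for the smallest subtype.** At 1:1 allocation, 72 is 36 per arm, against 95/2 = 47.5 at the floor. After 20% dropout: 0.8 × 36 = 28.8 per arm against 0.8 × 47.5 = 38.

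**Step 5: a trigger that holds.** Require 380 − 2T − 20 ≥ 95, so T ≤ (380 − 20 − 95)/2 = 132.5. At T = 132: 380 − 132 − 132 − 20 = 96, or 25.3%. Rescaling 144 as 40% of 380 would not help: 0.40 × 380 = 152, and 380 − 152 − 152 − 20 = 56, or 14.7%.

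**The case against.** **The figures are approximate.** Both the 25% and the 90 are qualified as approximate, and 23.7% or 24.2% is fairly read as about 25%. That stands, so the gap between 90 and 95 would hardly merit a comment alone. It does not stretch to 18.9%.

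**The trial need not close exactly at 380.** The paused subtypes stay closed until the lagging one reaches about 90, and some places in the protocol give the total as approximate or a minimum. Running on until the third subtype has 90 would end at 144 + 144 + 20 + 90 = 398, which is 4.7% over 380. The plan does not provide for this, and the share would still be 90/398 = 22.6%.

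**The worst case needs several things at once.** Two subtypes must be at or near their triggers with IBS-U near its cap. This is fair, and the documents give no expected split among the three major subtypes, so its probability cannot be computed. The trigger also suspends screening rather than randomisation, and the text is silent on subjects already in run-in, so 72 is not an exact bound. Such subjects could carry a subtype past 144 and leave fewer places.

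**No purpose is stated for the floor.** Nothing in the plan ties it to the subtype endpoints or powers them. This is correct and limits the weight of the point.

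**Two stronger readings are tempting but not supported.**

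- A reader might infer that the triggers were set for 360 subjects, because 90, 144 and the female stop of 270 are exactly 25%, 40% and 75% of 360. No section gives that total, and it would not explain the failure: at 360 the same worst case leaves 360 − 144 − 144 − 20 = 52 (14.4%). Nor would 270 of 360 correspond to 20% men, since it gives 25%.
- A reader might infer that the female stop ("Screening of female subjects will be discontinued if approximately 270 female subjects are randomized") forces the wrong sex ratio, since 380 − 270 = 110 men is 28.9%. But 20% men is a minimum, and 28.9% meets it. At the 60–65% women that Section 6.5 cites for IBS, 228–247 women are expected among 380. Even at 65%, a binomial calculation puts the chance of reaching 270 at about 0.7%. The stop is stricter than a 20% floor needs, but it is not an error.

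**Conclusion.** The point holds for the subtype rule. At 380, the triggers in Section 7.2.2 secure about 19% for the smallest major subtype in the worst case, not about 25%: 72 subjects against 95. Even where the pause works as written, release comes at 23.7%.

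This rests on three assumptions: enrolment closes at 380, the triggers act as counts of randomised subjects, and IBS-U fills to its cap. With no IBS-U subjects the worst case is 92 (24.2%), which the approximate wording can cover.

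The matter is minor. Sample composition and the precision of the subtype-specific secondary and subgroup analyses are affected; the primary test, alpha and the stated power are not.

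**What to change.** In Section 7.2.2, change two numbers: set the release level to about 95 and the pause trigger to about 132. With IBS-U capped at 20, the third subtype then keeps at least 96 places (25.3%), subject to overshoot from subjects already in run-in. The enrolment monitoring settings change to match.

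Alternatively, keep 144 and 90 and restate the commitment as the share they secure at 380, about 19% in the worst case.

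The first option may slow recruitment slightly, because a fast-enrolling subtype is paused earlier. The second costs only a sentence but gives up the 25% floor. The female stop needs no change on this account.

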7.2.3 Unblinding and Decoding Procedure

The study treatment blind shall not be broken unless information concerning the study treatment is necessary for the medical treatment of the subject. In the event of a medical emergency, if possible, the medical monitor should be contacted before the study treatment blind is broken to discuss the need for unblinding.

The sponsor must be notified as soon as possible if the study treatment blind is broken and record the date and time. The study treatment can be unblinded by the designated unblinded Curebase staff member. The reason, time and date the blind is broken must be recorded in the eCRF.

7.3 Participant compliance to Study Intervention

Curebase will store all study subject-reported data generated through the Curebase web application on a secure and HIPAA-compliant database. However, subject adherence data, defined as completion of required treatment sessions and numbers of practice sessions will be generated by our video server, Wistia. Wistia is a video hosting service that is able to securely keep and record detailed information about when and how long videos are accessed by a given user. Wistia-generated usage data is anonymously generated and stored and is transferred to metaMe through an API and matched to a subject ID (email address) on metaMe servers.

Linking usage data to email address is a necessary part of the metaMe notification and treatment tracking system. Usage data is used to generate adherence information that is in turn used to send reminders and prompts for a missed treatment session. Note that most other subject notifications like appointment reminders are generated based on the treatment schedule, not real-time adherence data. The adherence data is also used to ensure that the proper treatment content is available at the correct time and in the correct sequence. For example, the app may use the data from Wistia to determine if a session has been completed on the scheduled day; if it is not, the session remains available to the subject throughout the treatment window. If the session is completed, a practice session is made available the following day. Each day, all adherence data is transferred to the Curebase platform and stored. Curebase will provide long-term, HIPAA

compliant storage of adherence data for use in later analysis. Intervention compliance will be calculated by determining the number of completed treatment sessions and the number of completed practice sessions for each subject. We also will collect related contextual data, such as how much of the video was watched per attempt, whether the session was restarted at any point, whether the session was rescheduled, and whether the session was viewed late (after the scheduled day).

7.4 Concomitant Therapy

Requirements and proscriptions on concomitant therapy are outlined in the Inclusion/Exclusion Criteria ([Section 5.2](#) and [Section 5.3](#)).

Concomitant medication is any drug given in addition to the study treatment. These may be prescribed by a physician or obtained by the subject over the counter and are not provided by the sponsor. Subjects will be allowed to continue use of any concomitant IBS medications including probiotic supplements as permitted by the study inclusion and exclusion criteria. Subjects are required to maintain a stable dose during the treatment period unless otherwise advised by a physician. Changes to concomitant medications shall be evaluated at the predetermined timepoints. Dosage and frequency of treatment will be collected at the beginning of the study and again at week 8, 16, 38 and 64. Concomitant medication therapy will be coded using the WHO-DDE Medical Coding Dictionary.

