4.2.1 Primary Endpoint

The primary endpoint of this study is abdominal pain intensity. The Instrument is a 11-point numeric rating scale (0= no pain, 10= worst pain). The subject is asked to record their “*worst abdominal pain over the past 24-hours*”. An Abdominal Pain Intensity Responder is defined as a subject whose daily abdominal pain intensity averaged over the 4 weeks of Phase 3 (weeks 13 through 16) is 30% reduced compared to the daily abdominal pain intensity averaged over the 4 weeks of the Phase 1 (weeks -4 through -1).

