5 STUDY DESIGN

5.1 Overall Design

EASITx is a pivotal study of digital GDH (Regulora), a novel digital therapeutic that delivers the North Carolina GDH treatment protocol to IBS subjects. EASITx tests the hypothesis that the digital version of the North Carolina GDH treatment protocol is safe and, relative to a comparator treatment platform, enables a clinically significant reduction in abdominal pain intensity and other symptoms of IBS. EASITx is a pivotal medical device study, and digital GDH is classified as Software as a Medical Device (SaaMD).

The North Carolina GDH treatment protocol consists of 7 unique GDH scripts, each approximately 30 minutes in length and a single practice session, approximately 13 minutes in length. Each script has been converted to a video/audio recording allowing for administration via a mobile device, tablet, or personal computer, mimicking the frequency and duration of administration of therapist-administered GDH.

The EASITx study will apply state-of-the-art IBS and behavioral research methodology including use of a fully digital treatment platform, a comparator allowing for subject-blinding to treatment hypothesis, and a data collection (ePRO) system that allows for a double blind, eliminating the potential for investigator bias. The comparator-treatment platform will be identical to the GDH treatment platform, except that muscle relaxation (MR) audio recordings equal in treatment duration and frequency of administration will be substituted for the GDH video/audio recordings. MR was chosen as the control after consultation with the FDA.

Participation in the EASITx study will last 68 weeks and is divided into 4 phases:

- Phase 1: A 4-week pre-treatment run-in assessment period (weeks -4 through -1)
- Phase 2: A 12-week treatment period (weeks 1 through 12)
- Phase 3: A 4-week post-treatment assessment period (weeks 13 through 16)
- Phase 4: A 52-week post-treatment long term extension (LTE) during which time subjects will be required to complete two 4-week assessment periods starting 5 months post-treatment (weeks 35 through 38) and 11 months post-treatment (weeks 61 through 64).

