6.2 Inclusion Criteria

To be eligible to participate in this study, an individual must meet all of the following criteria, which are assessed at the Baseline Screening event (see previous section):

1. Provision of signed and dated informed consent form
2. Stated willingness to comply with all study procedures and availability for the duration of the study
3. Male or female, aged 18-70
4. Confirmation of the IBS and IBS subtype diagnosis by a study physician using Rome IV diagnostic criteria (see [Appendix A](#))
5. Possess an iOS or Android smartphone or an iOS tablet (iPad) released in 2015 or later.
6. Agreement to input information about their abdominal pain and bowel movements on a daily basis into Curebase software
7. Agreement to have their anonymized data stored in the cloud for up to 2 years after the conclusion of the study, and to have the data used for research purposes.

8. Agreement to maintain stable dosage of IBS medications during the course of treatment and not to add new IBS medication or stop current IBS medications unless directed to do so by the subjects treating physician. Changes in treatment will be captured using a concomitant medication assessment.

At the **Day 0 Screening** event, subjects must also meet the following criteria:

1. Average “Worst Daily Pain Severity” of ≥ 3 on an 11-point NRS over the full 28-day symptom tracking period
2. Consistent submission of Pain Severity scores via the Curebase app (data submitted on 70% or more of days in the symptom tracking window)

This study attempts to achieve excellent representation of women and minorities in the enrolled population, and there are no restrictions on eligibility based on the subject’s sex, gender, or race. Please see [Section 5.5](#) for information about how women and minorities will be recruited into the study.

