9.3 Populations for Analyses

Enrolled Population: The enrolled population will include all subjects who sign informed consent and meet the inclusion/exclusion criteria. This population will be used for evaluation of demographics and baseline characteristics.

Intent-to-Treat (ITT) Population: The ITT population will include all subjects who are randomized to treatment. Subjects that are replaced due to failed inclusion/exclusion criteria or technical issues in the Curebase software will be excluded. This population will be used for the evaluation of efficacy and all safety analyses.

Per Protocol (PP) Population: The PP population will consist of all subjects in the ITT population with no major protocol deviations that may affect efficacy. This population will be used as a supportive analysis of the primary endpoint.

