10.1.6.6 Protocol Deviations

A protocol deviation is any noncompliance with the clinical study protocol and ICH GCP requirements. The noncompliance may be either on the part of the subject, the investigator, or the study research staff. As a result of deviations, corrective actions are to be developed by the study physicians and implemented promptly.

These practices are consistent with ICH GCP:

- 4.5 Compliance with Protocol, sections 4.5.1, 4.5.2, and 4.5.3
- 5.1 Quality Assurance and Quality Control, section 5.1.1
- 5.20 Noncompliance, sections 5.20.1, and 5.20.2.

It is the responsibility of the study physicians and study monitors to use continuous vigilance to identify and report deviations within 10 working days of identification of the protocol deviation, or within 10 working days of the scheduled protocol-required activity. All deviations must be categorized as either significant or minor. Significant deviations are those events that cause or could cause harm to subjects or others or that affect the fidelity of the research. Curebase will maintain a database of protocol deviations for the duration of the study and shall be responsible for triaging report writing and internal documentation. Significant protocol deviations will be

sent to the reviewing Institutional Review Board (IRB) per their policies. The study physicians and study monitors are responsible for knowing and adhering to the reviewing IRB requirements.

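### The stable-dose rule for IBS medication ends with treatment at week 12, but the primary responder is scored on weeks 13–16; the rule should run to week 16

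*Combined protocol and SAP*

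**What the plan says.** - **Dose rule.** Section 7.4: "Subjects are required to maintain a stable dose during the treatment period unless otherwise advised by a physician". Inclusion criterion 8 (section 6.2) requires "Agreement to maintain stable dosage of IBS medications during the course of treatment". The same criterion adds a commitment not to start or stop IBS drugs unless the treating physician directs it.
- **Periods.** Section 5.1 lists "Phase 2: A 12-week treatment period (weeks 1 through 12" and, separately, "Phase 3: A 4-week post-treatment assessment period (weeks 13 through 16".
- **Primary endpoint.** Section 4.2.1 defines a responder as a subject whose "daily abdominal pain intensity averaged over the 4 weeks of Phase 3 (weeks 13 through 16) is 30% reduced" relative to the run-in.
- **Deviations and per-protocol set.** Section 10.1.6.6: "A protocol deviation is any noncompliance with the clinical study protocol and ICH GCP requirements". Section 9.3: "The PP population will consist of all subjects in the ITT population with no major protocol deviations that may affect efficacy". The supplied text does not say which deviations count as major.
- **Other therapy.** Section 7.4 says "Requirements and proscriptions on concomitant therapy are outlined in the Inclusion/Exclusion Criteria". Exclusion 4 (section 6.3) covers psychotherapy, hypnotherapy or CBT for IBS only if it is current.
- **Data capture.** Sections 7.4 and 8.5.1 collect concomitant medication at baseline and weeks 8, 16, 38 and 64, with drug start and end dates.

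**The concern.** The rule that holds background IBS medication constant stops where the scoring window opens. Medication changes after randomisation can depend on how the subject is doing, so they can differ by arm. More escalation in the MR arm shrinks the observed difference and costs power. More escalation in the GDH arm enlarges the difference and raises the chance of a false success.

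Counting outcomes regardless of added care is a legitimate choice for the primary analysis. However, the per-protocol analysis is meant to support it, and a change that breaks no rule is not a deviation that this set is required to remove.

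**Working it through.** **1. Windows side by side.** The stable-dose wording covers weeks 1–12 and the endpoint uses weeks 13–16, so none of the four scored weeks is covered by the phase definitions. The widest reading of treatment adds little. Seven sessions two weeks apart put session 7 on day 1 + 6 × 14 = 85, the first day of week 13, and the 3-day grace period reaches day 88. That leaves days 89–112, or 24 of the 28 scored days, uncovered.

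**2. The plan's own figure.** Inputs from section 9.2: 26% (MR) against 44% (GDH), 300 completers taken as 150 per arm, 5% level; two-sided from section 9.1. For a two-proportion z-test with pooled null variance:
- null SE = √(2 × 0.35 × 0.65 / 150) = 0.0551
- alternative SE = √(0.44 × 0.56/150 + 0.26 × 0.74/150) = 0.0541
- power = Φ((0.18 − 1.96 × 0.0551)/0.0541) = 90.9%, which agrees with the stated 90% or more.

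**3. How many escalators could convert.** The documents give no escalation rate or drug effect, so what follows rests on assumptions. A subject already improved by r₀, whose drug lowers pain by e over a fraction f of the window, responds if (1 − r₀)(1 − e·f) ≤ 0.70.

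| Dose raised at start of | f | e needed, r₀ = 0 | e needed, r₀ = 20% |
|---|---|---|---|
| Week 13 | 1.00 | 30% | 12.5% |
| Week 14 | 0.75 | 40% | 16.7% |
| Week 15 | 0.50 | 60% | 25% |
| Week 16 | 0.25 | 120% (impossible) | 50% |

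Assume that percent reduction is normal with SD 20–40 points, centred to give 26% or 44% responders, that start times are even over the window, and that escalators are a random sample of non-responders. Then:
- e = 10%: 4.3–8.8% of escalators convert in a 26% arm, 6.7–13.3% in a 44% arm.
- e = 20%: 9.6–20.1% and 14.4–28.1%.

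Conversion c of 10–20% is therefore the usable range; about 20% is the ceiling for a 26% arm.

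**4. Effect on the trial.** With x and y the shares of otherwise non-responders who escalate in the MR and GDH arms, MR = 0.26 + 0.74·x·c and GDH = 0.44 + 0.56·y·c.

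| Uptake MR / GDH | c | MR | GDH | Difference (points) | Power |
|---|---|---|---|---|---|
| none | – | 26.0% | 44.0% | 18.0 | 90.9% |
| 10% / 5% | 10% | 26.74% | 44.28% | 17.5 | 89% |
| 10% / 5% | 20% | 27.48% | 44.56% | 17.1 | 87% |
| 5% / 5% | 10% | 26.37% | 44.28% | 17.9 | 90% |
| 5% / 5% | 20% | 26.74% | 44.56% | 17.8 | 90% |
| 5% / 10% | 10% | 26.37% | 44.56% | 18.2 | 91% |
| 5% / 10% | 20% | 26.74% | 45.12% | 18.4 | 92% |

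**5. No true effect.** Both arms start at 26%, with uptake 5% MR / 10% GDH. Section 9.4.2 requires p < 0.05 and a difference of at least 10 points, so the chance of a GDH success is P(difference ≥ max(10 points, 1.96 × pooled SE)).
- No escalation: 2.42%.
- c = 10%: 26.37% against 26.74%, a 0.37-point difference; 2.95%.
- c = 20%: 26.74% against 27.48%, a 0.74-point difference; 3.47%.

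**The case against.** **The protocol may deal with this elsewhere.** It defers detail to a separate SAP that is not in the supplied text, and section 9 provides a blinded review of subject evaluability. A reader might infer that escalators certainly stay in the per-protocol set. The documents do not support that; they show only that no written rule removes them. Per-protocol is also not the only relevant analysis. Section 9.4.8 repeats the endpoint analyses by IBS drug use, and subjects on no IBS drug have no dose to raise. That is a partial check, depending on how drug use is defined. This objection stands and limits the claim.

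**The gap is narrow.** A reader might infer that every IBS treatment change in weeks 13–16 is unrestricted. The add/stop clause of criterion 8 has no clear end date, so starting or stopping a drug may still be barred. The position of newly started psychological therapy is also unclear. The firm claim concerns only a self-initiated dose increase of an existing drug. Physician-directed changes are allowed by design.

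**The effect may be close to nil.** A reader might infer a serious threat to the result. At 30% conversion the same formulas give 85% power and a 4.0% false-success chance, but 30% exceeds the ceiling of about 20% for a 26% arm. If the least-improved subjects are the ones who escalate, conversion falls further. At e = 20%, anyone below 12.5% improvement cannot convert even from the first day of week 13, and that is 55–79% of non-responders in a 26% arm under the same SDs. This also stands: the size is small.

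None of this closes the mismatch between the rule and the scoring window.

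**Conclusion.** The concern holds in a limited form. The stable-dose requirement misses the weeks that decide the trial, and a self-initiated increase of an existing IBS drug in those weeks breaches nothing written in the supplied text. The expected damage is modest: a loss of about 2 to 4 points of power if MR escalates more, or a rise of about 0.5 to 1 point in the chance of a false GDH success if GDH escalates more. Both depend on assumed uptake (5–10%) and conversion (10–20%), and the direction cannot be known in advance. This is a worthwhile, inexpensive improvement, not a flaw that undermines the primary analysis.

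**What to change.** **Reword criterion 8 (section 6.2 and the synopsis) and section 7.4.** From the start of treatment to the end of week 16, subjects keep IBS medication at a stable dose, do not start or stop IBS medication, and do not start psychological therapy for IBS, unless advised by a physician. This also settles the two unclear points about add/stop and psychological therapy.

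**Add two eCRF fields at weeks 8 and 16:** the date of any dose change, and whether a physician directed it. Section 8.5.1 lists neither. Without them an undirected change cannot be told from a permitted one, or reliably placed before or after week 12. With them, undirected changes can be identified as deviations and considered for exclusion from the per-protocol set.

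**Cost.** Four more weeks of restriction for subjects and the two fields. Sample size, visits and primary analysis are unchanged.

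**Optional.** A supportive analysis could score as non-responders all subjects who escalate between randomisation and the end of week 16. It must be read only beside the unchanged primary, because it can itself favour GDH. If a share u of MR and v of GDH subjects escalate, independently of response, then with no true effect it creates 0.26 × (u − v): 1.3 points at 10% / 5% and 2.6 points at 20% / 10%. Under the planned effect, heavier GDH uptake (5% / 10%) would instead cut the difference to 0.44 × 0.90 − 0.26 × 0.95 = 14.9 points.
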